### 4 weeks (T6)

#### +/- 5 days

- Perform alcohol breathalyzer to obtain BAC
- Collect urine for urine drug analysis and urine pregnancy test (if applicable)
- Collect blood, plasma and serum for CBD, Delta-9 THC, 11-Hydroxy Delta-9 THC, Delta-9 Carboxy THC and Anandamide levels (post- and pre-CBD levels)
- Collect blood for carbohydrate deficient transferrin (CDT) test
- · Record adverse events as reported by participant or observed by investigator
- Record vital signs, concurrent medications, menstrual calendar (if applicable), and results of evaluations of safety, psychomotor/subjective effects
- Evaluate and record alcohol use
- Evaluate and record AUD and PTSD-related measures
- Administer the cue/traumatic stress response task and record response
- Provide participants with sufficient study medication to administer daily until the next scheduled visit (2 weeks), and instructions for how to use the study medication and document their use
- Record participant's adherence to treatment program
- Administer medical management session

## 7.3.3.5 Phone call 2

#### 5 weeks (T7)

#### +/- 5 days

- Record adverse events as reported by participant
- Record participant's adherence to treatment program
- Record concurrent medications, menstrual calendar (if applicable), and results of evaluations of safety

## 7.3.3.6 Visit 8

6 weeks (T8)

+/- 5 days

- Perform alcohol breathalyzer to obtain BAC
- Collect urine for urine drug analysis and urine pregnancy test (if applicable)
- Collect blood, plasma and serum for CBD, Delta-9 THC, 11-Hydroxy Delta-9 THC, Delta-9 Carboxy THC and Anandamide levels(post- and pre-CBD levels)
- Collect blood for carbohydrate deficient transferrin (CDT) test and liver function tests (LFT)
- Record adverse events as reported by participant or observed by investigator
- Record vital signs, concurrent medications, menstrual calendar (if applicable), and results of evaluations of safety, psychomotor/subjective effects
- Evaluate and record alcohol use
- Evaluate and record AUD and PTSD-related measures
- Collect information for cognitive function changes
- Provide participants with morning dose of study medication at the study visit and 1 pill to take in the evening.
- Record participant's adherence to treatment program
- Administer medical management session

## 7.3.3.7 Visit 9

### 7 weeks (T9)

### +/- 5 days

- Perform alcohol breathalyzer to obtain BAC
- Collect urine for urine drug analysis and urine pregnancy test (if applicable)
- Collect blood and plasma for CBD, Delta-9 THC, 11-Hydroxy Delta-9 THC, Delta-9 Carboxy THC and Anandamide levels(pre-CBD levels)
- Collect blood for liver function tests (LFT)
- · Record adverse events as reported by participant or observed by investigator
- Record vital signs, concurrent medications, menstrual calendar (if applicable), results of evaluations of safety, psychomotor/subjective effects
- Evaluate and record alcohol use
- Evaluate and record AUD and PTSD-related measures

## 7.3.4 Final Telephone Follow-Up

## 9 weeks (T10)

#### +/- 5 days

- Record adverse events as reported by participant
- Evaluate and record alcohol use
- Record evaluations of safety
- Administer treatment completion questionnaires

## 7.3.5 Unscheduled Visit

Unscheduled visits will be documented on an unscheduled visit form.

#### 7.3.6 Clinical Re-Screen

If there is a delay of ~2-3 months between an eligible participant's screening visit and baseline visit, the following measures/procedures will be administered during a "clinical re-screen" at a separate visit or completed on the same day as the baseline visit (prior to baseline procedures) to confirm continued study eligibility as applicable:

The following measures/procedures will be conducted at the clinical re-screen:

- BAC
- Urine toxicology screen and urine pregnancy test (if applicable)
- PCL-5 (past month)
- TLFB (past 30 days)
- CIWA-Ar
- CSSRS (since last visit)
- Current medications

- Vital signs
- If determined necessary by the study clinicians, we may collect urine for urine analysis and blood at either the One Park site or at CTSI for hepatic function panel/liver function tests (LFT), complete blood count (CBC) with differential, basic metabolic panel, and serum pregnancy test (if female)

If there is a delay of over 3 months between an eligible participant's screening visit and their baseline visit, then the specific measures/procedures listed above (with the exception of the CSSRS since last visit) will be readministered. The LEC/CAPS5, CSSRS baseline/screening, and relevant sections of the SCID5 will also be readministered to confirm continued study eligibility and to confirm previously collected data. The TBI Ohio/CSI form will also be updated with any new head injuries. Re-screen procedures will be conducted remotely except blood draws and urine analysis, if applicable.

# 7.4 Concomitant Medications, Treatments, and Procedures

All concomitant prescription medications taken during study participation will be recorded on the case report forms (CRFs). For this protocol, a prescription medication is defined as a medication that can be prescribed only by a properly authorized/licensed clinician. Medications to be reported in the CRF are concomitant prescription medications, over-the-counter medications and non-prescription medications.

# 7.5 Prohibited Medications, Treatments, and Procedures

Treatment with medications acting on serotonergic pathways, cannabinoids, treatments for addictions including alcohol, and medications metabolized primarily by CYP3A4, CYP3A5, or CYP3A7 will not be permitted unless discussed with and approved by the PI.

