# 5.2 Exclusion Criteria

An individual who meets any of the following criteria will be excluded from participation in this study:

1. Current alcohol withdrawal (CIWA-Ar score >7)

2. Exclusionary medical conditions (e.g. current severe alcohol withdrawal requiring medical hospitalization, significantly impaired liver function)

3. DSM-5 diagnosis of schizophrenia, schizoaffective disorder, bipolar disorder I

4. High risk of adverse emotional or behavioral reaction, and/or an inability to understand study procedures or the informed consent process, based on investigator's clinical evaluation (e.g., evidence of serious personality disorder, antisocial behavior, serious current stressors, lack of meaningful social support)

5. Exposure to trauma in the last 30 days, including police duty or military service

6. Current significant suicidality (assessed using the C-SSRS), any significant suicidal behavior in the past 12 months, or any history of serious suicide attempts requiring hospitalization, or current significant homicidality

7. History of Severe Traumatic Brain Injury (TBI; as indicated by Loss of Consciousness > 24 hours)

8. DSM-5 diagnosis of current mild cannabis use disorder and/or moderate or severe substance use disorder for a substance other than alcohol or nicotine

9. Significant laboratory abnormalities, including significantly impaired liver function, serious abnormalities of complete blood count or metabolic panel

10. Active legal problems likely to result in incarceration within 12 weeks of treatment initiation

11. Pregnancy or lactation

12. Current use of exclusionary medications, including cannabinoids; treatments for addictions including alcohol; moderate to strong inhibitors of CYP3A4 or CYP2C19; medications metabolized primarily by CYP3A5 or CYP3A7; and medications with a narrow therapeutic index which are substrates of CYP3A4, UGT1A9, UGT2B7, CYP2C8, CYP2C9, CYP2C19, CYP1A2, or CYP2B6.

13. Current treatment for AUD (with exceptions of: AA/12-step treatment and/or psychosocial treatment initiated more than 2 months prior to the screening visit)

14. Current treatment for methadone or opioid abuse

15. Psychotherapy for PTSD or other psychiatric condition, if initiated within 2 months of screening

16. Inpatient psychiatric treatment in the last 12 months, with the exception of detox and extended Emergency Department stays

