## 5.7 Participant Withdrawal or Termination

#### 5.7.1 Reasons for Withdrawal or Termination

Participants are free to withdraw from participation in the study at any time upon request. An investigator may terminate participation in the study if:

• Any clinical adverse event (AE), laboratory abnormality, or other medical condition or situation occurs such that continued participation in the study would not be in the best interest of the participant

- The participant meets an exclusion criterion (either newly developed or not previously recognized) that precludes further study participation
- The participant fails to adhere to protocol requirements

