#### 6.1.8 **Dose Adjustments/Modifications/Delays**

If participants report AEs that are determined by the PI to be treatment-related during administration of study medication and are intolerable to the participant or represent a significant risk to the participant, daily administration will be reduced by 200mg/day every two days until symptoms are tolerable or clinical abnormalities are resolved. For self-described symptoms, tolerability will be determined by a joint decision between the PI and the participant, based upon of whether this symptom is tolerable or treatment related. For laboratory abnormalities, all values outside of the normal range will be regarded as presenting a risk, as evaluated by the PI. All reported AEs will be recorded. Dose will be titrated back up toward the full dose by 200 mg/day/week as tolerated, based upon a repeat assessment by the PI, including laboratory tests.

Individuals who cannot tolerate the 600mg dose will remain on their maximum tolerable dose for the remainder of the study. Treatment will be discontinued immediately if continuing the medication places the participant at significant risk in the medical judgement of the PI.

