## 6.3.1 Administration of Intervention

CBD (or placebo) will be administered daily for 6 weeks. The first administration of CBD vs. placebo (at T1) will take place at the study site. Participants will remain at the study site with a study team member for approximately 2 hours following the initial administration of each dose of CBD, and participants will not be permitted to leave the study site until they are able to pass a standard field sobriety test (a walk-and-turn task, one-leg stand, Romberg's test, finger-finger test, and counting backwards [85]). If there are no AEs during this time-period or lasting intoxicating effects of the study drug (i.e. participants are able to pass field sobriety tests 2-3 hours after study drug administration), participants will be given a 1- or 2-week supply of the study drug (CBD or placebo) to self-administer daily at home until the next scheduled study visit.

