# **12 Monitoring Adverse Events**

The investigator will follow all AEs until the event is resolved, stabilized, or the subject is lost to follow-up. Relevant
clinical assessments and laboratory tests may be performed as determined by the PI or a qualified designee, appropriate medical intervention should be provided and, if necessary, the subject may be excluded from additional treatment with the study drug.

Any actions taken and follow-up results must be recorded on the appropriate page of the CRF and in the subject's source documentation. Follow-up laboratory results should be filed with the subject's source documentation.

For all AEs that require the subject to be discontinued from the study, relevant clinical assessments and laboratory tests will be repeated as clinically appropriate, until final resolution or stabilization of the event(s).

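### Section 7.5 omits two drug-interaction classes that exclusion criterion 12 bars at entry, so such a drug could be started during dosing with no approval step in the protocol

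*Combined protocol and SAP*

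**What the plan says.** **At entry.** Section 5.2, criterion 12, excludes people currently using certain medications. Besides cannabinoids and addiction treatments, it has three drug-interaction clauses. The first two are "moderate to strong inhibitors of CYP3A4 or CYP2C19; medications metabolized primarily by CYP3A5 or CYP3A7". The third is "medications with a narrow therapeutic index which are substrates of CYP3A4, UGT1A9, UGT2B7, CYP2C8, CYP2C9, CYP2C19, CYP1A2, or CYP2B6".

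**On study.** Section 7.5 lists serotonergic drugs, cannabinoids, addiction treatments and one interaction class: "medications metabolized primarily by CYP3A4, CYP3A5, or CYP3A7 will not be permitted unless discussed with and approved by the PI". It does not refer back to criterion 12. Section 7.4 requires concomitant medications to be recorded and sets no approval step.

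**Possible responses elsewhere.**
- Section 5.7.1: "An investigator may terminate participation in the study if" one of several conditions applies, among them "The participant meets an exclusion criterion (either newly developed or not previously recognized) that precludes further study participation".
- Section 6.1.8: "Treatment will be discontinued immediately if continuing the medication places the participant at significant risk in the medical judgement of the PI".
- Section 12 (Monitoring Adverse Events): "if necessary, the subject may be excluded from additional treatment with the study drug".

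**Setting.** After the first supervised dose, section 6.3.1 provides that "participants will be given a 1- or 2-week supply of the study drug (CBD or placebo) to self-administer daily at home".

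**The concern.** The plan itself treats these drug classes as unsuitable alongside CBD when a participant enters. The list that site staff would consult during treatment does not repeat two of them. A participant who begins a CYP2C19 inhibitor or a narrow-index CYP2C9 substrate in week 3, say, would not breach 7.5 unless the drug also fell in a class that 7.5 names. Nothing in the protocol would require anyone to agree to the combination beforehand.

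This is a safety matter. Study drug is taken at home, so the team may first hear of the new drug at the next contact that records medications, after the two have been taken together. Narrow-index drugs are the ones with the least room for altered exposure, which is presumably why criterion 12 singles them out.

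**Working it through.** The protocol gives no figure to reproduce here. The check compares the two lists clause by clause, looks for a safeguard elsewhere, and then considers how soon a new drug would come to light.

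**Step 1: the clauses side by side.**

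| Interaction clause in 5.2 no. 12 | Carried into 7.5? |
|---|---|
| (a) Moderate or strong inhibitors of CYP3A4 or CYP2C19 | No: 0 of 2 enzymes |
| (b) Drugs cleared mainly by CYP3A5 or CYP3A7 | Yes: 2 of 2, subject to PI approval |
| (c) Narrow-index substrates of eight enzymes | As worded, no. In effect, CYP3A4 only, and only where CYP3A4 is the primary route: 1 of 8 |

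For clause (c), 8 − 1 = 7 enzymes have no counterpart in 7.5: CYP1A2, CYP2B6, CYP2C8, CYP2C9, CYP2C19, UGT1A9 and UGT2B7. One clause is therefore carried over, one is absent, and one is largely absent.

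**Step 2: does criterion 12 run on by itself?** It is worded as current use, within the conditions for being excluded from participation. Where an exclusion is meant to continue, the protocol says so: criterion 17, on opioid-positive urine screens, names later visits. Criterion 12 has no such wording.

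**Step 3: does another section supply a prohibition or a prior approval?**
- 5.7.1 permits termination for a newly developed exclusion. It is discretionary and applies once the criterion is already met.
- 6.1.8 makes stopping study drug mandatory, but only once the PI has judged the risk significant.
- Section 12 concerns the follow-up of adverse events.
- 7.4 concerns recording only.

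None of them bars the drug or requires agreement before it is combined with study drug.

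**Step 4: when would a new drug be noticed?** The schedule in section 7.3 records concurrent medications at B1, T2, T3, T4, T5, T6, T7 and T8, which is 8 contacts. T3 to T8 fall at weeks 1, 2, 3, 4, 5 and 6, so the scheduled spacing from T3 on is 7 days.

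**Step 5: who is exposed?** Thirty participants are expected on CBD for 6 weeks. The documents give no rate at which these drugs are started, so no number affected can be derived.

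**The case against.** The strongest reply is that 7.5 should not be read alone. A newly developed exclusion criterion is a stated ground for ending participation, and 6.1.8 obliges the PI to stop study drug when the risk is significant. That stands as far as it goes: the plan does not endorse these combinations. But both provisions act after the event, and the first is optional.

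Second, 7.5 is in places broader than criterion 12. It covers every drug metabolised mainly by CYP3A4, narrow-index or not, and all serotonergic drugs. Some drugs in the omitted classes will therefore still need approval. This is correct and narrows the gap by an unknown amount.

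Third, the inhibitor clause may matter less than the narrow-index clause. If the worry is higher CBD exposure, the dose rationale in section 2 reports daily doses up to 1000 mg as tolerated in trials, against 600 mg here. The documents do not say how far an inhibitor would raise exposure, so this tempers the point without settling it.

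Two stronger readings are tempting. A reader might infer that the trial has no advance-notice step at all. The documents do not support that: the consent form, SOPs and manual of procedures are not available, and the schedule mentions instructions given with study medication. A reader might also stretch the 7-day spacing using the ±5 day windows, to 7 + 5 = 12 days if windows run from the previous contact, or 7 + 5 + 5 = 17 days if they run from B1. The second needs one contact at its earliest limit and the next at its latest. The documents do not say how the windows are counted, and this extreme should not be presented as the usual delay.

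**Conclusion.** The point holds as an internal inconsistency with a safety consequence: the on-treatment rule is looser than the entry rule for two of the three interaction clauses in criterion 12. The gap covers moderate or strong CYP3A4 or CYP2C19 inhibitors, and narrow-index substrates of the seven enzymes other than CYP3A4, except where a particular drug also falls in a class that 7.5 names.

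The finding about the protocol's wording is certain. What happens in practice is less so, because it depends on documents not seen and on an unknown rate of starting such drugs. It would be wrong to infer that participants were or will be harmed, or that a large share of the 30 on CBD is at risk; nothing in the documents gives a figure for either. Severity is minor to should-fix.

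**What to change.** Add to section 7.5:

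1. The drug-interaction classes in exclusion criterion 12 are also not permitted from B1 through T8 unless the PI has discussed and approved the drug before its first dose.
2. Participants are told to contact the study team before starting any new drug.
3. Medications already recorded at B1 and T2 to T8 are checked against this list.
4. If such a drug is medically necessary, the PI decides and documents whether study drug is continued, reduced or stopped. A participant whose study drug is stopped stays in follow-up and in the ITT analysis.

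This uses the approval mechanism that 7.5 already has. An outright ban on every class in criterion 12 would clash with the existing approvable status of CYP3A4-metabolised drugs. Automatic stopping of study drug is also best avoided: section 6.1.9 ties inclusion in the primary analyses to completing the 6-week treatment phase, so a default stop could remove participants from a 48-person trial. Item 4 follows the ITT population in 20.3.1 instead and should say so. Section 15.4 already uses stop-drug-but-follow for pregnancy.

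The cost is one short amendment, a little extra PI review and an occasional stop of study drug. No new data collection is needed.

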# 8 Definitions of Key Terms

An adverse event (AE; also referred to as an adverse event) is any untoward medical occurrence associated with the use of a drug (pharmaceutical investigational product) in humans, which does not necessarily have a causal relationship with that treatment. An AE can therefore be any unfavorable and unintended sign (e.g., an abnormal laboratory finding or test result), symptom, disease, accident, or worsening (increase in severity or frequency) of a pre-existing abnormality, temporally associated with the use of the drug, whether or not considered related to the drug. An AE can arise from any use of the drug (e.g., off-label use, use in combination with another drug and from any route of administration, formulation, or dose, including overdose).

A serious adverse event (SAE) is an adverse drug or biologic or device experience occurring during any study phase (i.e., screening, admission, treatment, or follow-up), and at any dose of the study drug, comparator or placebo, that results in one or more of the following criteria:

- Results in death
- Is life-threatening\*
- Requires in-patient hospitalization (i.e., admission) or prolongation of existing hospitalization
- Results in persistent or significant disability\*\* or incapacity
- Is a congenital abnormality or birth defect (in an offspring)
- Is an important medical event that may not result in death, be life-threatening, or require or prolong hospitalization may be considered an SAE when, based upon appropriate medical judgment, the event may jeopardize the subject or may require medical or surgical intervention to prevent one of the outcomes listed above. Examples of important medical events include events requiring intensive treatment in an emergency department, convulsions that do not require in-patient hospitalization, or the development of drug dependency or drug abuse (see Section 8, Other Significant Adverse Events).

\*Life-threatening: Any AE that places the subject, in the view of the investigator, at immediate risk of death from the reaction as it occurred; it does not include a reaction that, had it occurred in a more severe form, might have caused death.

\*\*Disability: A substantial disruption of a person's ability to conduct normal life functions.

# 9 Specification of Safety Variables

Safety and toxicity monitoring will be performed throughout the study for all subjects. Safety variables to be assessed include AEs, vital signs, and safety laboratory values, when collected.

The occurrence of an AE or SAE may come to the attention of study personnel during study visits and interviews of a study participant presenting for medical care, or upon review by a study monitor. At each study visit following screening, designated study team members will inquire about the occurrence of AE/SAEs since the last visit.

# **10 General Guidelines**

All AEs, regardless of causality or severity, must be immediately recorded on the AE CRF when volunteered by the subject or solicited through a study assessment questionnaire. The CRC will record all AEs, regardless of causality or severity, with start dates occurring any time after informed consent is obtained until 7 (for AEs) or 30 (for SAEs) days after the last day of study participation on the AE case report forms (CRF). Information to be collected includes event description, time of onset, clinician's assessment of severity, relationship to study product (assessed only by those with the training and authority to make a diagnosis), and time of resolution/stabilization of the event.

Any medical condition that is present at the time that the participant is screened will be considered as baseline and not reported as an AE. However, if the study participant's condition deteriorates at any time during the study, it will be recorded as an AE.

Changes in the severity of an AE will be documented to allow an assessment of the duration of the event at each level of severity to be performed. AEs characterized as intermittent require documentation of onset and duration of each episode.

At the last scheduled visit, the CRC should instruct each subject to report any subsequent event(s).

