## 5.7.2 Handling of Participant Withdrawals or Termination

Every effort will be made to undertake the protocol-specified safety follow-up procedures to capture AEs, SAEs, and UPs. The investigator will attempt to obtain at a minimum safety/survival data on all participants lost to follow-up. If a participant is lost to follow-up, they study team will attempt to contact the participant up to 15 times by telephone, email, or text message. If the participant fails to respond, locators identified by the participant at screening will be contacted up to three times in the method specified by the participant. If participants withdraw, are terminated, or are lost to follow-up prior to the end of the 6-week treatment phase (prior to T8), they will not be replaced to maintain 48 randomized participants to complete the 6-week treatment phase (through T8) and their partial data will be handled according to the statistical analysis plan (SAP).

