#### 6.1.9 **Duration of Therapy**

The duration of the active treatment portion of the study is 6 weeks, followed by an additional 3-week followup period. In order for participants to be included in the primary statistical analyses, they must complete the 6week treatment phase of the study (through to T8).

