### 20.3.2 Analysis of the Primary Endpoint(s)

For Hypothesis 1a, Safety and tolerability, the frequency of adverse events will be analyzed for the entire sample at all time points, tabulated for each treatment group, and compared using chi-squared tests. The safety analysis will be largely descriptive of outcomes for the entire study population. The incidence of AEs will be summarized by system organ class, preferred term, the likelihood of its relationship to the treatment, and severity for each treatment group. Clinical laboratory data will be summarized by type of test. Frequency and percentage of patients whose values fall outside of reference ranges will be presented for each measurement.

For Hypothesis 1b, Alcohol Use. The Primary outcome measure, number of drinks per day, will be analyzed with an MMRM to assess differences in change from baseline. The primary contrast is change from baseline (B1) at week 6 (T8). The model at each time point will include terms for treatment, time and treatment by time interaction as factors and the baseline value for each score as a covariate. Parameter estimation will be based on REML and to begin an unstructured covariate matrix will be used. If the model fails to converge, the form of the covariance matrix will be chosen based on Akaike's Information Criteria, and Schwarz' Bayesian Criterion. Model-based LS means will be obtained for change from baseline to each time point for each treatment group. At each time point, contrasts between CBD and placebo will be obtained. Secondary alcohol use measures will be tested with MMRM sequentially in a closed testing union intersection paradigm in the order listed in section C.8.3. Validity of the p-value will extend until the first test fails to have a p-value smaller than a two-sided alpha of 0.05. The analyses will continue for all measures but the resulting p-value will be nominal.

For Hypothesis 2, PTSD symptoms, the primary outcome measure, total score of the PCL-5, will be analyzed in the same way as the primary outcome for alcohol use. The primary contrast is change from baseline (B1) at week 6 (T8).

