#### 20.3.4 Safety Analyses

Means and standard deviations of plasma CBD and THC levels within the CBD treatment group will be presented following 45 minutes (T1), 1 day (T2), 1 week (T3), 2 weeks (T4), 4 weeks (T6),6 weeks (T8) of treatment with CBD vs. placebo, and one week (T9) after the completion of treatment to determine whether target plasma levels of CBD have been achieved, and whether metabolic transformation of CBD to THC has occurred.

The number of participants within each treatment group that were able to pass a battery of psychomotor field sobriety tasks (walk-and-turn task, one-leg stand, Romberg's test, finger-finger test, and counting backwards

[85]) within 2 hours of the initial administration of CBD vs. placebo (T1) will be analyzed as summary statistics during treatment.

AEs and SAEs, when present, will be collected on an AE Case Report Form at study visits. The form will include an assessment of clinical significance and study relatedness. Serious Adverse Events (SAEs) will be documented on an additional SAE form. These CRFs will be based on those used in recent NIDA Clinical Trials Network trials. To further assess abuse potential, visual analog scales will be used to assess abuse potential. Scales will include desire to use the study medication again, desire to use the study medication again for pleasurable intoxication ("to get high"), and craving for the study medication.

The study may be stopped if there are untoward and concerning levels of Adverse Event (AE) or Serious Adverse Event (SAE) outcomes attributable to CBD or study participation. If the DSMB finds it is likely that CBD is contributing to negative outcomes, they will consider solutions including protocol changes or potentially stopping the study.

The frequency of adverse events will be analyzed for the entire sample tabulated for each treatment group and compared using chi-squared tests. The safety analysis will be largely descriptive of outcomes for the entire study population. The incidence of AEs will be summarized by system organ class, preferred term, the likelihood of its relationship to the treatment, and severity for each treatment group. Clinical laboratory data will be summarized by type of test. Frequency and percentage of patients whose values fall outside of reference ranges will be presented for each measurement.

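### The between-arm AE comparison has no treatment-emergent window and no allowance for unequal observation, so pre-dose and off-drug time dilute a true on-drug difference

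*Combined protocol and SAP*

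**What the plan says.** Section 10 (General Guidelines) has AEs recorded "with start dates occurring any time after informed consent is obtained", and ends recording "until 7 (for AEs) or 30 (for SAEs) days after the last day of study participation". The end is thus tied to each participant's own last day, a term the protocol does not define, and not to a dose or a study week.

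Section 6.1.9 sets the planned course: "The duration of the active treatment portion of the study is 6 weeks, followed by an additional 3-week followup period". The last scheduled AE contact is the week 9 telephone call (T10, section 7.3.4).

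Section 20.3.2 says "the frequency of adverse events will be analyzed for the entire sample at all time points, tabulated for each treatment group", with chi-squared tests. Section 20.3.4 repeats it: "The frequency of adverse events will be analyzed for the entire sample tabulated for each treatment group and compared using chi-squared tests". Neither gives a treatment-emergent window, a safety population, a counting unit (participants or events), person-time or a time-to-event method. Section 20.3.5 tallies discontinuations but does not use them in the AE comparison.

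For those who leave, section 5.7.2 says "Every effort will be made to undertake the protocol-specified safety follow-up procedures to capture AEs, SAEs, and UPs" and "The investigator will attempt to obtain at a minimum safety/survival data on all participants lost to follow-up". Section 6.1.9 also limits the primary statistical analyses to participants who complete treatment through T8, which does not fit an AE analysis of the entire sample. Section 20.1 leaves a formal SAP to be written before database lock and unblinding.

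**The concern.** AEs are listed among the primary endpoints in the Protocol Summary, and section 20.3.8 hypothesises no difference between arms on safety. Anything that pulls the AE comparison toward no difference therefore favours the expected conclusion.

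Two features could do so. The first needs no dropout: time before the first dose and after the last dose is pooled with time on drug, and in that time the arms should have the same AE risk. The second is conditional: if a leaver's recording stops soon after exit, observation time depends on an event after randomisation. An arm that loses more people then has less time in which AEs can be counted.

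**Working it through.** The protocol gives no AE rate and no dropout rate by arm, so there is no figure of its own to reproduce. The hazards and dropout rates below are assumptions, shown as ranges. AE times are exponential, and the chance of at least one AE is 1 − exp(−H), where H is the summed weekly hazard.

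**Observation time (sections 6.1.9, 7.3.4, 10).** Completer: 6 + 3 + 1 = 10 weeks after first dose, 4 of them off drug. Someone who leaves at week 2 and gives no further data: 2 + 1 = 3 weeks.

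**A. No dropout.** Placebo hazard h per week; CBD hazard 1.5h on drug and h off drug.

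At h = 0.10:
- On drug only, 6 weeks: CBD 1 − exp(−0.90) = 59.3%; placebo 1 − exp(−0.60) = 45.1%; difference 14.2 points.
- Planned window, 10 weeks: CBD 1 − exp(−(0.90 + 0.40)) = 72.7%; placebo 1 − exp(−1.00) = 63.2%; difference 9.5 points. Rate ratio 1.30/1.00 = 1.30 instead of 1.50, and it is 1.30 at any h.
- If 4 pre-dose weeks are counted too (baseline is 1 to 30 days after screening, section 7.3.2): 1 − exp(−1.70) = 81.7% v 1 − exp(−1.40) = 75.3%; difference 6.4 points.
- First dose to last dose plus 7 days: 1 − exp(−(0.90 + 0.10)) = 63.2% v 1 − exp(−0.70) = 50.3%; difference 12.9 points.

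The same formulas over a range of h:

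| h per week | On drug, 6 weeks | Planned window, 10 weeks |
|---|---|---|
| 0.03 | 7.2 points | 6.4 points |
| 0.07 | 12.4 | 9.4 |
| 0.10 | 14.2 | 9.5 |
| 0.15 | 14.7 | 8.1 |

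**B. No drug effect; dropout 30% CBD v 10% placebo at week 2, unrelated to AEs; no data after exit plus 7 days.** Share with an AE = d·F(3) + (1 − d)·F(10), where d is the dropout share and F(t) = 1 − exp(−ht).
- h = 0.03: 20.7% v 24.2%, difference −3.5 points.
- h = 0.07: 40.9% v 47.2%, −6.3.
- h = 0.15: 65.3% v 73.5%, −8.3.
- Event-count ratio: (0.7·10 + 0.3·3)/(0.9·10 + 0.1·3) = 7.9/9.3 = 0.85 instead of 1.00.

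**C. Where B does not apply.**
- Equal dropout: no bias when there is no drug effect.
- Dropout reversed (10% v 30%): the same figures with the opposite sign.
- AEs early (80% of the hazard in weeks 0 to 2): bias 0.8 to 1.3 points.
- The AE itself causes the exit: the share with an AE hardly moves (simulated 50.2% to 50.4% at h = 0.07 as dropout rises from 0 to 27%). Event counts per participant do fall (0.70 to 0.58).

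**D. Both effects, h = 0.10, 1.5-fold on-drug hazard.** CBD leavers 1 − exp(−(0.30 + 0.10)) = 33.0%; placebo leavers 1 − exp(−0.30) = 25.9%. At 30% v 10% dropout: 0.7·72.7 + 0.3·33.0 = 60.8% v 0.9·63.2 + 0.1·25.9 = 59.5%, difference 1.3 points. Of the fall from 14.2 points, 4.7 come from off-drug time with no dropout (14.2 − 9.5); the remaining 8.2 come from the assumed dropout (9.5 − 1.3).

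**The case against.** - **Leavers are not abandoned.** Section 5.7.2 promises safety follow-up for people who withdraw or are terminated, with up to 15 contact attempts and then locators. Section 20.3.5 separates stopping the intervention from stopping follow-up, and section 15.4 keeps follow-up going after drug is stopped for pregnancy. Someone who stops capsules but stays to T10 has the full window. This stands: the short window is a risk from an undefined term and imperfect follow-up, not a planned feature.
- **The dropout bias assumes that leaving is unrelated to AEs**, although the worry is that the drug drives people out. This stands for the share of participants with any AE. It does not rescue event counts, and a person who leaves for one AE cannot contribute a later, different one to the preferred-term tables.
- **Pre-dose AEs may never enter the comparison.** Sections 4.2.1 and 7.1.3 describe AE collection at visits after treatment starts. This is fair, and makes the 6.4-point figure an outer case. But section 10 starts at consent and section 20.3.2 sets no onset rule, so the text does not settle it.
- **The safety analysis is largely descriptive and the trial is small.** With 30 v 18 participants and an AE share near 60%, the 95% margin is about 1.96·√(0.6·0.4·(1/30 + 1/18)) = ±29 points. True; no test here will turn on a few points. The estimate is still what the trial passes on, and a systematic shrinkage is avoidable.
- **Person-week rates are not a clean cure.** With the early-AE pattern, no drug effect and 30% v 10% dropout, a first-dose to last-dose-plus-7-days rate gives [(0.7·0.925 + 0.3·0.825)/(0.7·7 + 0.3·3)] / [(0.9·0.925 + 0.1·0.825)/(0.9·7 + 0.1·3)] = 1.11 against CBD. This stands, so the rate should not be reported alone.
- **A formal SAP is still to come.** It could settle all of this, which is a reason to raise it now.

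**Conclusion.** The point holds in a limited form. As written, the AE comparison mixes on-drug time with about 4 off-drug weeks per completer, and possibly with pre-dose time. If CBD raises AE risk only while it is taken, this pulls the comparison toward no difference without any dropout. With a 1.5-fold on-drug hazard the rate ratio appears as 1.30. The difference in participants with an AE falls from 14.2 to 9.5 points at a placebo hazard of 0.10 per week, and the loss runs from 0.8 points at 0.03 to 6.6 points at 0.15.

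A reader might go further and infer that early leavers are bound to have the shortest window and that CBD will therefore look safer. The documents do not support that. They do not predict more dropout on CBD, and section 5.7.2 intends follow-up after exit. The shift of 3.5 to 8.3 points needs three things together: higher dropout on CBD (30% v 10% here), exits not triggered by the AE, and follow-up that fails. Otherwise it is near zero, or reversed if placebo loses more people.

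**What to change.** - **Collection.** Keep AE recording at least as long as now. Define a participant's last day so that withdrawn participants who can be reached are followed for AEs on the same study clock as completers, as section 5.7.2 intends.
- **Population.** Use all dosed participants for the AE comparison, and state that the completer rule in section 6.1.9 does not apply to safety.
- **Window.** For the arm comparison, count AEs with onset from first dose to last dose plus 7 days. Tabulate pre-dose and later off-drug AEs separately. This window is still shorter for those who stop early, which is why the next item is needed.
- **Measures.** State the counting unit. Beside the planned table of participants with at least one AE, give time to first AE (Kaplan-Meier) by arm, and events per person-week with a rate ratio and 95% CI that allows for repeat events. Note that the rate assumes a constant hazard.

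Cost: wording in section 20.3 and the coming SAP, and slightly more analysis. Section 10 already collects onset times. The first dose is given on site (section 6.3.1), but the last-dose date must be derived from dosing videos, pill counts and returned medication (sections 6.2 and 6.3.2).
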